11.1.4 RECIST Response Criteria

11.1.4.1 Evaluation of Target Lesions

Complete Response (CR): Disappearance of all target lesions. Any pathological lymph nodes (whether target or non-target) must have reduction in short axis to <10 mm.

Partial Response (PR): At least a 30% decrease in the sum of the diameters of target lesions, taking as reference the baseline sum diameters.

Progressive Disease (PD): At least a 20% increase in the sum of the diameters of target lesions, taking as reference the smallest sum on study (this includes the baseline sum if that is the smallest on study). In addition to the relative increase of 20%, the sum must also demonstrate an absolute increase of at least 5 mm. (Note: the appearance of one or more new lesions is also considered progressions).

Stable Disease (SD):

Neither sufficient shrinkage to qualify for PR nor sufficient increase to qualify for PD, taking as reference the smallest sum diameters while on study.

11.1.4.2 Evaluation of Non-Target Lesions

Complete Response (CR):

Disappearance of all non-target lesions and normalization of tumor marker level. All lymph nodes must be non-pathological in size (<10 mm short axis).

Note: If tumor markers are initially above the upper normal limit, they must normalize for a patient to be considered in complete clinical response.

Non-CR/Non-PD:

Persistence of one or more non-target lesion(s) and/or maintenance of tumor marker level above the normal limits.

Progressive Disease (PD):

Appearance of one or more new lesions and/or *unequivocal progression* of existing non-target lesions. *Unequivocal progression* should not normally trump target lesion status. It must be representative of overall disease status change, not a single lesion increase.

Although a clear progression of “non-target” lesions only is exceptional, the opinion of the treating physician should prevail in such circumstances, and the progression status should be confirmed at a later time by the review panel (or Principal Investigator).

11.1.4.3 Evaluation of Best Overall Response

The best overall response is the best response recorded from the start of the treatment until disease progression/recurrence (taking as reference for progressive disease the smallest measurements recorded since the treatment started). The patient's best response assignment will depend on the achievement of both measurement and confirmation criteria.

For Patients with Measurable Disease (*i.e.*, Target Disease)

Target Lesions	Non-Target Lesions	New Lesions	Overall Response	Best Overall Response when Confirmation is Required*
CR	CR	No	CR	≥4 wks. Confirmation**
CR	Non-CR/Non-PD	No	PR	≥4 wks. Confirmation**
CR	Not evaluated	No	PR	
PR	Non-CR/Non-PD/not evaluated	No	PR	
SD	Non-CR/Non-PD/not evaluated	No	SD	Documented at least once ≥4 wks. from baseline**
PD	Any	Yes or No	PD	no prior SD, PR or CR
Any	PD***	Yes or No	PD	
Any	Any	Yes	PD	

* See RECIST 1.1 manuscript for further details on what is evidence of a new lesion.
** Only for non-randomized trials with response as primary endpoint.
*** In exceptional circumstances, unequivocal progression in non-target lesions may be accepted as disease progression.

Note: Patients with a global deterioration of health status requiring discontinuation of treatment without objective evidence of disease progression at that time should be reported as “*symptomatic deterioration*.” Every effort should be made to document the objective progression even after discontinuation of treatment.

For Patients with Non-Measurable Disease (*i.e.*, Non-Target Disease)

Non-Target Lesions	New Lesions	Overall Response
CR	No	CR
Non-CR/non-PD	No	Non-CR/non-PD*
Not all evaluated	No	not evaluated
Unequivocal PD	Yes or No	PD
Any	Yes	PD

* 'Non-CR/non-PD' is preferred over 'stable disease' for non-target disease since SD is increasingly used as an endpoint for assessment of efficacy in some trials so to assign this category when no lesions can be measured is not advised

11.1.5 Choi Criteria

Table 3. Modified CT Response Evaluation Criteria	
Response	Definition
CR	Disappearance of all lesions No new lesions
PR	A decrease in size* of $\geq 10\%$ or a decrease in tumor density (HU) $\geq 15\%$ on CT No new lesions No obvious progression of nonmeasurable disease
SD	Does not meet the criteria for CR, PR, or PD No symptomatic deterioration attributed to tumor progression
PD	An increase in tumor size of $\geq 10\%$ and does not meet criteria of PR by tumor density (HU) on CT New lesions New intratumoral nodules or increase in the size of the existing intratumoral nodules

Abbreviations: CR, complete response; PR, partial response; HU, Hounsfield unit; CT, computed tomography; SD, stable disease; PD, progression of disease; RECIST, Response Evaluation Criteria in Solid Tumors.

*The sum of longest diameters of target lesions as defined in RECIST.¹⁰

11.1.6 Duration of Response

Duration of overall response: The duration of overall response is measured from the time measurement criteria are met for CR or PR (whichever is first recorded) until the first date that recurrent or progressive disease is objectively documented (taking as reference for progressive disease the smallest measurements recorded since the treatment started).

The duration of overall CR is measured from the time measurement criteria are first met for CR until the first date that progressive disease is objectively documented.

Duration of stable disease: Stable disease is measured from the start of the treatment until the criteria for progression are met, taking as reference the smallest measurements recorded since the treatment started, including the baseline measurements.

11.1.7 Progression-Free Survival

PFS is defined as the duration of time from start of treatment to time of progression or death, whichever occurs first.

11.1.8 Response Review

N/A

12. DATA REPORTING / REGULATORY CONSIDERATIONS

Adverse event lists, guidelines, and instructions for AE reporting can be found in Section 7.0 (Adverse Events: List and Reporting Requirements).

12.1 Data Reporting

12.1.1 Method

Electronic case report forms (eCRFs) will be created by SARC, the overall Principal Investigator and reviewed by the statistician. The database will be built within the Medrio system for data collection for this study.

The definition of serious adverse events (SAEs) is given in Section 7.1. Each serious adverse event must be followed up until resolution or stabilization, by submission of updated reports to the designated person. CTCAE v 5.0 grade 3 or 4 baseline laboratory abnormalities that are part of the disease profile should not be reported as an SAE, specifically when they are allowed or not excluded by the protocol inclusion / exclusion criteria.

When required, and according to local law and regulations, serious adverse events must be reported to the IRB and Regulatory Authorities.

All serious adverse events should be reported to SARC within 24 hours. In the event of such an event, the investigator should refer to the Adverse Reporting section of the Operations Manual for reporting procedures.

The Investigator will report serious adverse events (SAEs) using the MedWatch 3500A form.

All reports shall be sent electronically to SARC:

SARC: [name]

SARC will send the SAE reports and coversheets to Immunocore within 1 working day.

12.1.2 Pregnancies

The investigator must report to SARC any pregnancy occurring in a study subject, or in his partner, during the subject's participation in this study. The report should be submitted within the same timelines as an SAE, although a pregnancy per se is not considered an SAE.

For a study subject, the outcome of the pregnancy should be followed up carefully, and any abnormal outcome of the mother or the child should be reported.

For the pregnancy of a study subject's partner, all efforts should be made to obtain similar information on course and outcome, subject to the partner's consent. Please see section 7.2.3 with more information regarding pregnancy.

12.1.3 Further safety documentation

Progressive disease

If progressive disease leads to signs and symptoms that meet the criteria for an SAE (i.e., hospitalization, disability, death, or important medical event), the signs and symptoms should be reported as an SAE and not the underlying progressive disease.

Death

If any subject dies during the trial or within 30 days of the end-of-treatment visit, the investigator will inform SARC and record the cause of death in detail (using the SAE Form) within 24 hours.

12.1.4 Patient Accrual and Participating Centers

There will be approximately 4 centers collaborating to accrue patients to this study. We anticipate accrual will take approximately 3 years.

This trial will be posted at the www.clinicaltrials.gov website.

12.2 Data Safety and Monitoring

SARC is responsible for the Data Safety Monitoring for this trial. SARC Clinical Trials Review Committee convenes monthly and will provide safety oversight for this trial. The purpose of the Clinical Trials Review Committee is to review the status of the on-going SARC studies, which includes, but is not limited to:

- o Review of all safety data (Serious Adverse Events reported).
- o Review of protocol deviations/violations.
- o Review of study progress/accrual.
- o Discussion of statistical aspects of all protocols.

The committee is chaired by the SARC Medical Officer, who is responsible for leading the meeting and providing medical oversight. Attendance includes all overall study Principal Investigators on active SARC studies, SARC Research Project Managers, and a biostatistician.

12.3 Multi-Institutional Guidelines

The trial coordinating center (Operations Center) will be SARC. Patients will be registered electronically via the study website and adverse events (as defined in section 7.0) will be reported to the SARC Operations Center.

IRB approvals:

The protocol must be approved by the treating institution prior to enrolling patients. Documentation of individual IRB approval for the current protocol must be provided to the SARC Operations Center prior to enrolling patients on the trial. In addition, documentation of approval of all protocol amendments and of yearly continuing review must be provided to the Research Project Manager electronically via email.

Patient Registration:

Patient registration will be centrally managed electronically via the study website (see section 4.2).

Data Collection and Toxicity Reporting:

Registration reports will be generated by the Operations Center to monitor patient accruals and completeness of registration data. Routine data quality reports will be generated to assess missing data and inconsistencies by the SARC. Any potential problems will be brought to the attention of the study Principal Investigator(s) for discussion and action.

Access to the password protected study database will be limited to individuals involved in the clinical trial including: SARC staff, overall Study PI, participating site PIs, research nurse and data managers responsible for this trial.

Shipment and receipt of specimens and imaging studies sent for correlative studies will be entered and tracked on the study database. Details regarding handling and shipping will be outlined in the study operations manual.

12.4 Data and Participating Institution Monitoring

Data monitoring for this trial will be managed remotely. A data monitoring and site monitoring plan will be developed for this trial. Should areas of concern be identified through the remote monitoring process, an on-site monitoring visit may be warranted. Findings will be discussed with the overall study PI, participating site PIs, Clinical Trials Review Committee and the SARC medical officer.

12.5 Human Subjects Protection

12.5.1 Rationale for Subject Selection

Subjects of both genders and from all racial and ethnic groups are eligible for this trial if they meet the eligibility criteria as outlined in section 3.1. No groups will be excluded from participation in the trial.

12.5.2 Evaluation of the Benefits and Risks/Discomforts

The primary risk to patients participating in this research study is from toxicity associated with tebentafusp.

12.5.3 Management of Patient Data

All patient data will be captured and maintained in a study specific database with password-protected access. Data is entered using an assigned study subject identification number.

The data provided to those reviewing the results, for example the study statistician will include the subject identification numbers but will not include patient identifiable data.

The research samples obtained on this study will only be sent using the study subject identification number, which can only be linked to the patient at a given institution by the treating physician.

All documentation that contains personal health information that may include patient identifiable information will be maintained at the site to preserve patient confidentiality.

12.6 Premature termination of study

This study may be closed prematurely for any of the following reasons:

If risk-benefit ratio becomes unacceptable owing to, for example:

- Safety findings from this study (e.g. SAEs)
 - Results of any interim analysis
 - Results of parallel clinical studies
 - Results of parallel animal studies
- (on e.g. toxicity, teratogenicity, carcinogenicity or reproduction toxicity).
- If the study conduct (e.g. recruitment rate; drop-out rate; data quality; protocol compliance) does not suggest a proper completion of the trial within a reasonable time frame.
 - The investigator has the right to close his/her center at any time.

For any of the above closures, the following applies:

- Closures should occur only after consultation between involved parties.
- All affected institutions (e.g. IEC(s)/IRB(s); competent authority(ies); study center; head of study center) must be informed as applicable according to local law.

In case of a partial study closure, ongoing subjects, including those in post study follow-up, must be taken care of in an ethical manner. Details for individual subject's withdrawal can be found in Section 5.

13. STATISTICAL CONSIDERATIONS

13.1 Study Design/Endpoints

This will be a multi-center open label phase II study of tebentafusp in patients with unresectable or metastatic CCS. CCS is an orphan disease with few efficacious systemic

treatment options and few standard of care treatment options in the unresectable or metastatic setting. This study will assess for a signal of efficacy of a novel immunotherapeutic agent (tebentafusp) in the HLA-A*02:01-positive patients and simultaneously prospectively measure real-world outcomes in the HLA-A*02:01-negative patients.

The primary endpoint is to estimate PFS rate at 24 weeks, as determined by RECIST 1.1. In the CREATE trial (one of the few prospective clinical trials in this disease), the PFS rate at 6 months (PFS₆) for patients with advanced CCS treated with crizotinib was approximately 25%.⁹ In other prospective and retrospective studies of alternative systemic therapies, the median PFS was between 2 and 3 months and the PFS₆ was not reported.^{6,8,32}

Van Glabbeke and colleagues³³ have previously described appropriate thresholds for PFS₆ in the design of phase II studies in soft tissue sarcoma patients refractory to first-line treatment. Based on historical controls, they conclude a PFS₆ of 8% is not promising and PFS₆ of 14% to be promising.³³ Based on all of the above, we believe PFS₆ is an appropriate and meaningful clinical endpoint in this patient population. We will consider a 10% PFS₆ as not promising and 30% to be promising.

Simon's two-stage minimax design³⁴ will be used. The null hypothesis that the true PFS rate at 24 weeks is 10% will be tested against a one-sided alternative that it is 30%. In the first stage, 13 patients will be accrued. If ≤ 1 of the first 13 patients enrolled is progression-free at 24 weeks, the protocol will stop enrolling patients due to futility. Otherwise, 10 additional patients will be accrued for a total of 23 patients treated. The study will be claimed positive if 5 or more of 23 patients are progression-free at 24 weeks. This design yields a one-sided type I error rate of 0.1 and power of 0.84.

All patients who have received at least one dose of study therapy will be assessable for safety. Patients evaluable for efficacy analysis will include all patients treated with tebentafusp who are assessable for response. Patients who have no assessment of response post-baseline will not be considered evaluable for response unless they missed the assessment due to progression of disease or death, in which case they will be considered non-responders for that time point. Patients with at least one post-baseline assessment who are not assessed at 24 weeks for reasons other than progression of disease, death, will be evaluated based on their last imaging assessment. For example, patients with excessive toxicity will be censored at the date of their most recent disease evaluation prior to receiving any future systemic treatment regimens. Patients who are not evaluable (excluding those who died, had progression of disease, stopped study treatment due to treatment-related toxicity, or those with at least one post-baseline assessment) may be replaced.

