2. BACKGROUND

2.1 Study Disease

Clear Cell Sarcoma

An Ultra-rare Soft Tissue Malignancy with No Clearly Effective Treatments

In 1965, Franz Enzinger, a pathologist at the Armed Forces Institute of Pathology (AFIP), described a new subtype of sarcoma based on a histologic review of 21 cases of soft tissue tumors of the tendons or aponeuroses. Microscopically, he described tumors with pale fusiform cells of epithelioid appearance with clear cytoplasm and minute vacuoles arranged in nests and fascicles. The cellular aggregates were enclosed by septa of fibrous

connective tissue that were continuous with dense collagenous structures of tendinous or aponeurotic tissue. He named these tumors clear cell sarcomas of the tendons and aponeuroses (CCS). Clinically, they were characterized by “slow but relentless growth” with a tendency to recur and metastasize.³

Enzinger later published a larger series of 141 CCS patients in collaboration with Chung, reporting a median age of 27 years at diagnosis, a clear predilection for the extremities (97% of primary tumors), and a slight predominance among women. 24% of the study population were alive with recurrent or metastatic disease and an additional 35% died of metastases. The mean interval from the time of surgical resection to the first recurrence was 2.6 years.⁴ WeAn even larger retrospective of 489 patients from the National Cancer Database found 38% of patients had stage IV disease at diagnosis. The median overall survival (OS) of all patients from diagnosis was 57.2 months; those with stage IV disease had a dismal median survival of 8.9 months.⁵

There is no standard of care treatment for patients with advanced CCS. One report led by The Royal Marsden Hospital found of 24 CCS patients treated with traditional cytotoxic chemotherapy in the first-line metastatic setting, only one (4%) achieved a partial response (PR). In the second line, there were zero objective responses and only 8% of patients achieved stable disease (SD). The median progression-free survival (PFS) was 2.5 months and the median OS was 9 months.⁶ Similar outcomes were reported by investigators at the Gustave Roussy Institute in France.⁷ Most recently, Smrke and colleagues at the Royal Marsden led an international retrospective study of 55 patients with advanced clear cell sarcoma. The median PFS was reported to be 4 months with a median overall survival of 15 months.⁸

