3. PATIENT SELECTION

3.1 Eligibility Criteria

- 3.1.1 Age \geq 18 years
- 3.1.2 Histologically confirmed diagnosis of HMB-45+ clear cell sarcoma which is unresectable and/or metastatic
- 3.1.3 HLA-A*02:01 positive
- 3.1.4 ECOG Performance Status of \leq 2 at screening
- 3.1.5 At least one site of measurable disease on CT/MRI scan as defined by RECIST v 1.1 criteria. Baseline imaging must be performed within 28 days of Cycle 1 Day 1 of study.
- 3.1.6 Adequate organ function within 28 days of Day 1 of study defined as:
 - Absolute Neutrophil Count (ANC) \geq 1.5
 - Platelets \geq 75
 - ALT and AST \leq 2.5 x institutional upper limit of normal (ULN) or \leq 5.0 x institutional ULN if considered due to tumor
 - Alkaline phosphatase \leq 2.5 x institutional ULN unless considered due to tumor
 - Serum bilirubin \leq 1.5 x institutional ULN. **NOTE:** Patients with elevated bilirubin secondary to Gilbert's disease are eligible to participate in the study

- Serum creatinine $\leq 1.5 \times$ institutional ULN or 24-hour creatinine clearance ≥ 50 ml/min (calculated creatinine clearance using Cockcroft formula is acceptable)
- 3.1.7 Written, voluntary informed consent
- 3.1.8 Patients must demonstrate progression of disease by RECIST 1.1 within 6 months of study enrollment. Newly diagnosed patients with unresectable or metastatic disease and only one baseline scan are eligible to screen and enroll.
- 3.1.9 All other relevant medical conditions must be well-managed and stable, in the opinion of the investigator, for at least 28 days prior to first administration of study drug

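### Section 13.1 supports the 10% null with a median PFS that section 2.1 contradicts, leaves the cited 25% rate unreconciled, and prints the type I error ceiling of 0.1 where the attained value is 0.068.

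*Protocol*

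**What the plan says.** Protocol section 13.1 builds the null from three pieces of evidence.

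- **Crizotinib trial.** The six-month PFS rate "for patients with advanced CCS treated with crizotinib was approximately 25" percent. Section 2.1 describes this trial as 26 patients with MET-expressing tumours and a median PFS of 4.3 months.
- **Other studies (references 6, 8 and 32).** "In other prospective and retrospective studies of alternative systemic therapies, the median PFS was between 2 and 3 months", with no six-month rate reported.
- **General soft tissue sarcoma thresholds.** 8% is not promising and 14% is promising, for use "in the design of phase II studies in soft tissue sarcoma patients refractory to first-line treatment".

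It then concludes: "We will consider a 10% PFS₆ as not promising and 30% to be promising". The test is set up accordingly: "The null hypothesis that the true PFS rate at 24 weeks is 10% will be tested against a one-sided alternative that it is 30" percent.

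The rule is Simon's minimax design. Accrual stops for futility if at most 1 of 13 patients is progression-free at 24 weeks. Otherwise it continues to 23, and the trial is positive with 5 or more. Of this rule 13.1 says: "This design yields a one-sided type I error rate of 0.1 and power of 0.84". The synopsis makes the same statement.

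Section 2.1 describes reference 8, the 55-patient international retrospective series, differently: "The median PFS was reported to be 4 months with a median overall survival of 15 months".

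**The concern.** The text that justifies the null contains a figure that another section contradicts. The discrepancy makes past outcomes look worse, which favours a low null. A reader relying on 13.1 alone would not learn that the larger of the two retrospective series whose median PFS section 2.1 reports has a median of 4 months.

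Separately, 10% is well below the one disease-specific six-month rate cited, and no sentence connects the two. What is at stake is the meaning of a positive trial: rejecting 10% could be taken as activity beyond what the protocol already reports for crizotinib.

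Finally, a printed operating characteristic is inexact. The protocol says the design yields 0.1, and the rule it specifies does not.

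**Working it through.** **1. The two passages on reference 8.** Section 13.1 (citing references 6, 8 and 32): 2 to 3 months. Section 2.1, reference 8: 4 months. Section 2.1, reference 6 (24 patients): 2.5 months. Reference 6 fits the range in 13.1 and reference 8 does not. The protocol gives no separate figure for reference 32.

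**2. Operating characteristics of the rule.** Inputs from 13.1: n1 = 13, stop if X1 ≤ 1; n2 = 10; positive if X1 + X2 ≥ 5; p0 = 0.10; p1 = 0.30.

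P(positive | p) = Σ over x ≥ 2 of P(X1 = x | 13, p) × P(X2 ≥ 5 − x | 10, p), where the second factor is 1 for x ≥ 5.

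| Stage 1 count | p = 0.10 | p = 0.25 | p = 0.30 |
|---|---|---|---|
| x = 2 | 0.2448 × 0.0702 = 0.0172 | 0.2059 × 0.4744 = 0.0977 | 0.1388 × 0.6172 = 0.0857 |
| x = 3 | 0.0997 × 0.2639 = 0.0263 | 0.2517 × 0.7560 = 0.1902 | 0.2181 × 0.8507 = 0.1856 |
| x = 4 | 0.0277 × 0.6513 = 0.0180 | 0.2097 × 0.9437 = 0.1979 | 0.2337 × 0.9718 = 0.2271 |
| x ≥ 5 | 0.0065 | 0.2060 | 0.3457 |
| **P(positive)** | **0.068** | **0.692** | **0.844** |

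- The stated power of 0.84 reproduces.
- The stated type I error of 0.1 does not. Nearby readings do not give it either: single stage with 5 of 23, 0.073; success at 4 or more, 0.164; success at 6 or more, 0.022.
- Read as a ceiling, 0.1 is consistent. An exhaustive search for error ≤ 0.10 and power ≥ 0.84 returns this same design as minimax (smallest total, then smallest expected sample size under the null).

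**3. What the cut-off means against the cited 25%.** If the true 24-week rate is 25%, the trial is claimed positive with probability 0.69. The smallest positive result is 5/23 = 21.7%, exact 95% CI 7.5% to 43.7% (ordinary binomial interval, ignoring the interim look). That point estimate is below 25%.

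**4. What the cited medians imply at 24 weeks.** The protocol gives no curves, so a shape must be assumed. With S(t) = 0.5^((t/m)^k) and t = 24 × 7/30.4375 = 5.52 months, take k = 1 (exponential) and k = ln 2/ln(6/4.3) = 2.08. The latter fits the crizotinib trial's own pair of a 4.3-month median and 25% at six months.

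| Median m | k = 1 | k = 2.08 |
|---|---|---|
| 4 months (reference 8 in 2.1) | 38% | 26% |
| 2.5 months (reference 6 in 2.1) | 22% | 2.7% |

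The 4-month median implies a rate above 10% under either shape. The 2.5-month median falls on either side of 10%, depending on the shape.

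**The case against.** The case for leaving 10% alone is substantial, and much of it stands.

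- **Not every cited benchmark exceeds 10%.** Section 2.1 reports no responses and only 8% stable disease in second-line chemotherapy, which implies a 24-week rate of about 8% or less. The 2.5-month median can fall below 10%, and 10% lies between the general thresholds of 8% and 14%. A reader might infer that the null is below all the disease-specific evidence; the documents do not support that.
- **The 25% is imprecise and selected.** It comes from 26 MET-expressing patients given a MET inhibitor. Assuming 6 or 7 of 26, the exact 95% CIs are 9.0% to 43.6% and 11.6% to 47.8%. A Simon null is an uninteresting rate, not the best result seen with another agent. The protocol says it seeks a signal of efficacy, does not claim superiority to crizotinib, and plans comparisons with historical controls and an HLA-negative cohort in 13.4.
- **The type I error discrepancy is conservative.** A reader might infer that a positive result means less because 0.1 does not reproduce. The reverse holds: at 10% the chance of a false claim is 0.068, smaller than printed.
- **Six months versus 24 weeks.** A reader might infer that thresholds set for six-month PFS are tested at an easier time point. But the hypotheses are already stated at 24 weeks, and scans are fixed to C1D1. After week 24 the next scheduled scan is week 30 (± 7 days), later than six months (about 26.1 weeks), so as measured here the two rates could differ only through deaths or unscheduled findings.
- **Population.** Section 3.1.8 adds that "Newly diagnosed patients with unresectable or metastatic disease and only one baseline scan are eligible to screen and enroll", which might suggest the refractory-disease thresholds do not apply. Other patients must show RECIST progression within 6 months, and the expected share of newly diagnosed patients is not given, so a misapplication is not shown.
- **A higher bar for the crizotinib comparison.** Requiring 9 of 23 would hold the error at 0.096 against 25%, but power would be only 0.23 at a true 30% and 0.61 at 40%. It is not a useful addition.

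None of this removes the contradiction over reference 8, the silence between 10% and 25%, or the inexact error rate.

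**Conclusion.** The point holds as a correction of the justification and of the stated claim, not as a fault in the design. Sections 13.1 and 2.1 disagree on reference 8 (2 to 3 months against 4 months). The attained type I error is 0.068 against a printed 0.1, and power of 0.844 agrees with the printed 0.84. These results follow from the protocol's text and exact binomial arithmetic.

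The limit on interpretation is also exact, given the rule: probability 0.69 of a positive claim at a true 24-week rate of 25%, with 21.7% as the smallest positive proportion. How much weight it deserves depends on taking the cited 25%, an imprecise six-month figure, as a reference value at 24 weeks. Only the rates derived from medians rest on assumed curve shapes. A 10% null remains defensible for signal-finding in an ultra-rare disease, but 13.1 does not make that argument in light of the 25%.

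**What to change.** Keep 13 and 23 patients and the cut-off of 5 of 23, and change the wording as follows.

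- **(a)** Reconcile the reference 8 median between 13.1 and 2.1 after checking the source. The protocol alone does not show which figure is right, so neither should simply be copied across.
- **(b)** In 13.1 and the synopsis, state the attained one-sided type I error as 0.068 (ceiling 0.10), with power 0.84.
- **(c)** State in 13.1 that meeting the criterion of 5 or more of 23 supports only a 24-week rate above 10% and does not in itself show activity beyond the cited 25%. A sentence on why 10% was chosen despite that figure would complete the justification.

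The cost is a few sentences in an amendment, with no patients added and no change to the decision rule. The one consequence is a more modest claim when the result is at or near the cut-off.

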10.3 END OF TREATMENT EVALUATIONS

Final visit is to be performed at the time (or within 14 days after treatment stop date). End of treatment evaluations will include:

- Review of concomitant medications including any prior medications taken
- Physical exam (short)
- Vital signs (pulse, blood pressure, temperature, respiratory rate, and oxygen saturation).
- Relevant laboratory evaluations
 - Complete blood count with differential
 - Comprehensive metabolic panel (sodium, potassium, chloride, bicarbonate, BUN, creatinine, glucose, total protein, albumin, total bilirubin, total protein, AST, ALT, alkaline phosphatase, calcium), magnesium, and phosphorus

- Amylase, lipase, CK, and LDH
- PT (or INR) and aPTT
- Thyroid function tests (TSH, T4 free, T3)
- Urinalysis (dipstick)
- Serum β-HCG or urine pregnancy test for women of child-bearing potential. If the urine test is positive or cannot be confirmed as negative, a serum pregnancy test is required
- Research biopsy (if feasible)
 - EOT biopsy should be collected within 21 days of treatment stop or prior to starting next line of therapy.
- Research blood collection

Patients who complete study treatment should be followed for survival every 12 weeks until death, study withdrawal, or study end. Survival data can be collected by phone or EMR.

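### The last-scan rule for a missing week-24 assessment conflicts with its own censoring example and can turn an early drop-out with stable disease into a 24-week success

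*Protocol*

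**What the plan says.** Section 13.1 of the protocol sets a Simon two-stage test of a 10% against a 30% progression-free rate at 24 weeks. "In the first stage, 13 patients will be accrued"; accrual stops if at most 1 of them is progression-free at 24 weeks. Otherwise 10 more are added, and "The study will be claimed positive if 5 or more of 23 patients are progression-free at 24 weeks". The stated properties are a one-sided type I error of 0.1 and power of 0.84.

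The same section then deals with missing week-24 data. Patients scanned at least once after baseline "who are not assessed at 24 weeks for reasons other than progression of disease, death, will be evaluated based on their last imaging assessment". The sentence that follows is offered as an example of this rule: "patients with excessive toxicity will be censored at the date of their most recent disease evaluation prior to receiving any future systemic treatment regimens". Patients with a post-baseline assessment are excluded from replacement. Section 13.4.2 (Evaluation of response) keeps everyone who did not withdraw before starting treatment in the primary analysis. These patients therefore stay among the 23.

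Scans are due every 6 weeks through week 48 (Section 2.4), so the last scheduled scan before week 24 can be at week 6, 12 or 18.

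**The concern.** The rule already sets aside patients whose assessment is missing because of progression or death. For those who remain, the last scan will normally not show progression. If that scan decides the patient's status, stable disease at week 6 stands in for an observation 18 weeks later and counts toward the 5 needed. If the censoring sentence governs instead, the patient is neither a success nor a failure, and a count out of 23 has no such category. One reading inflates the count and the other leaves it undefined.

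This affects both the futility look and the final claim. With a threshold of only 5 successes, one misclassified patient matters. The protocol itself fixes the rule, so a separate analysis plan would have to contradict the protocol to repair it.

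**Working it through.** **Inputs, all from Section 13.1:** p0 = 0.10, p1 = 0.30; stage 1 n = 13, stop if ≤1; stage 2 adds 10; positive if ≥5 of 23.

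**Formula.** P(positive | p) = Σ over x = 2..13 of P(X1 = x; 13, p) × P(X2 ≥ 5 − x; 10, p).

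**Reproducing the plan's figures**
- Power at p = 0.30: 0.844, which agrees with the stated 0.84.
- Type I error at p = 0.10, term by term: x = 2: 0.2448 × 0.0702 = 0.0172; x = 3: 0.0997 × 0.2639 = 0.0263; x = 4: 0.0277 × 0.6513 = 0.0180; x ≥ 5: 0.0065. The sum is 0.068. The stated 0.1 is a ceiling or a one-decimal rounding, not the exact value.

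**One automatic success, all others at 10%**
- In stage 1, at least 1 of the other 12 is needed to continue and 4 more successes overall: 0.0264 + 0.0607 + 0.0555 + 0.0256 = 0.168. The chance of passing the futility look rises from 0.379 to 1 − 0.9^12 = 0.718.
- In stage 2, at least 2 of 13 are still needed to continue and 4 in total from 13 + 9: 0.0551 + 0.0611 + 0.0342 = 0.150.
- Against the stated 0.1 this is 1.5 to 1.7 times; against the exact 0.068 it is 2.2 to 2.5 times.

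**Two automatic successes:** 0.352 (both in stage 1), 0.337 (one per stage), 0.273 (both in stage 2).

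**Per-patient rate d of leaving this way (assumed; the protocol gives none).** If leaving is independent of outcome, the apparent null rate is 0.1(1 − d) + d.
- d = 2%: 0.118, type I error 0.118
- d = 5%: 0.145, type I error 0.219
- d = 10%: 0.190, type I error 0.428

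**Timing of the last scan (assumed exponential PFS with 10% at week 24).** A patient stable at week w reaches week 24 with probability 0.1^((24 − w)/24): 0.18 for w = 6 and 0.56 for w = 18. The fair comparator scores that patient by the true outcome. For a stage 1 patient at week 6 it is 0.18 × 0.168 + 0.82 × 0.057 = 0.077, so the rule multiplies the error by 2.2 (2.0 in stage 2). At week 18 the comparator is 0.56 × 0.168 + 0.44 × 0.057 = 0.119, and the factor is about 1.4. The 0.057 is the type I error when that patient counts as a failure.

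**If such patients count as not progression-free**
- One: type I error 0.057-0.059, power 0.808-0.820.
- Two: type I error 0.047-0.050, power 0.766-0.791.

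**The case against.** The protocol never says that these patients are successes, and its own example censors those with toxicity. That stands: the documents support saying that such patients can count as successes, not that they certainly do. It does not rescue the rule, because the count still has no place for a censored patient.

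A reader might infer from Section 10.3, "Patients who complete study treatment should be followed for survival every 12 weeks until death, study withdrawal, or study end", and from a calendar with no scan marked at end of treatment or follow-up, that nobody is scanned once treatment stops. The protocol as a whole does not support this. Section 5.3 says that patients who discontinue are not withdrawn and should return for the Section 11 assessments. Section 11.1 sets 6-weekly re-evaluation, and Section 11.1.4.3 asks that objective progression be sought after discontinuation. These places need reconciling, but they do not show that missing week-24 scans will be common.

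A reader might also list symptomatic deterioration ("Patients with a global deterioration of health status requiring discontinuation of treatment without objective evidence of disease progression") among the drop-outs scored as successes. Section 7.1.1.6 bases a determination of clinical progression on such deterioration, so these patients are arguably outside a rule limited to reasons other than progression.

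Frequency may also be low. The only related rate in the protocol is 2% discontinuation for related adverse events in the tebentafusp group of the uveal melanoma trial (Sections 2.2 and 5.1.2). At 2% the type I error is 0.118, close to the stated limit. Withdrawals and new therapy would add to that rate by an unknown amount.

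Finally, this is a single-arm phase II study seeking a signal of efficacy, not a confirmatory trial. That is fair, but this is still its one formal decision rule.

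**Conclusion.** Wrong as written. The last-scan sentence and the censoring example contradict each other, and neither maps onto the ≤1 of 13 and ≥5 of 23 rules. On the plain reading, one early drop-out with stable disease takes the type I error to 0.150-0.168, above the stated 0.1, and two take it to 0.27-0.35.

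It is tempting to say that one such patient more than doubles the type I error. That holds only against the exact 0.068, which the protocol does not state; against the stated 0.1 the factor is 1.5 to 1.7. These figures assume a true rate of 10% and a patient who would otherwise have had a 10% chance of success. The effect of the rule is smaller when the last scan is late. The number of such patients is an assumption throughout.

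**What to change.** Replace the last-scan sentence in Section 13.1 with wording such as: For the stage 1 and final counts, a patient is progression-free at 24 weeks only with a non-PD RECIST 1.1 assessment at week 24 (±7 days) or later, before any new systemic anticancer therapy; all other treated patients in the primary analysis set count as not progression-free. Keep censoring at the last scan for the Kaplan-Meier PFS analysis, and report the Kaplan-Meier 24-week estimate as a sensitivity analysis.

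Reconcile Section 10.3 and the study calendar with Sections 5.3, 11.1 and 11.1.4.3, so that the protocol says in one way which tumour assessments continue after treatment stops without progression.

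The cost is an amendment to the wording, possibly some further scans depending on how those sections are reconciled, and some power: from 0.844 to 0.81-0.82 with one such patient and to 0.77-0.79 with two. The type I error stays below 0.1 in each case. Accepting a later non-PD scan limits the loss when a week-24 scan is missed for administrative reasons.
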